3.3. STUDY DESCRIPTION AND RATIONALE

This study is a prospective open-label study in which Pocket-X Gel will be applied to periodontal pockets in one/two mouth segments of participants following scaling and root planing on the entire mouth, while the contralateral segment(s) of the mouth will serve as control.

The purpose of this study is to examine the safety and efficacy of Pocket-X Gel in the treatment of periodontal pockets, following scaling and root planing procedure.

The study's hypothesis is that Pocket-X Gel, when inserted into periodontal pockets following scaling and root planing procedure, would lead to greater improvement in periodontal clinical measurements such as pocket depth, bleeding upon probing, clinical attachment level, etc., in comparison to periodontal pockets which have undergone scaling and root planing only.

Pocket-X Gel is inserted into the periodontal pockets as a liquid. Following application, the product quickly transforms into a gel, due to contact with body temperature, and adheres to the inner lining of the periodontal pockets. This *in-situ* transformation from liquid form to gel allows Pocket-X Gel to fit into periodontal pockets of all sizes while completely filling the pockets. It is hypothesized that Pocket-X Gel, once inside the periodontal pocket, would act as a physical barrier against infiltration of bacteria originating from the oral cavity into the pocket, thus contributing to the greater improvement in the clinical state of the periodontal pocket.

The preceding procedure, scaling and root planing, is a conservative treatment which is considered the gold standard treatment of periodontitis in the majority of cases. As part of this procedure, the patient undergoes mechanical debridement which removes subgingival plaque and tartar, resulting in significant reduction of the bacterial load in the periodontal pockets. Subsequently, the inflammation in the area subsides, which allows the gingiva to initiate its natural healing process and seal the pockets.

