9. STUDY ASSESSMENTS

9.1. EFFICACY ASSESSMENT

The following measurements will be recorded during the study, and will be used to assess the efficacy of the intervention:

- Plaque index
- Pocket probing depth
- Bleeding index
- Recession level
- Clinical attachment level
- Mobility grade
- Furcation
- Specific periodontal bacteria quantification [optional]

The above measurements will be recorded at baseline and at follow-up visits for each participant. The values will be recorded separately for each periodontal pocket. .

Efficacy data from follow-up visits will be compared to the baseline values in order to obtain the efficacy results. The efficacy results will be compared between treated periodontal pockets and control periodontal pockets and to data obtained from available literature.

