15. STATISTICAL ANALYSIS

15.1. SAMPLE SIZE CONSIDERATION

The rationale for sample size was based on demonstrating a difference in change in pocket depth between the tested segments and the control, reflecting effect size of 0.5 with 80% power and 5% significance level.

Effect size is defined as the difference in change between the treatments adjusted to standard deviation, and calculated as follows:

$$\frac{(\text{Change from baseline in Test segments} - \text{Change from baseline in Control segments})}{\text{Common standard deviation of the change}}$$

Sample size Justification *

A sample size of 27 will have 80% power to detect an effect size of 0.5 using a Paired t-test with a 0.05 one-sided significance level.

Assuming ~20% dropout rate, 34 subjects will be recruited, in order to have 27 participants who complete the study.

Reference:

* Additional sample size justification presents the same sample size and effect size, but specifies the expected changes within each treatment and the common standard deviation:

A sample size of 27 will have 80% power to detect a difference in means of -0.5 (e.g. a First condition mean, μ_1 , of 2.0 and a Second condition mean, μ_2 , of 2.5), assuming a standard deviation of differences of 1.0, using a paired T-test with a 0.05 one-sided significance level.

The calculations are summarized in the table below:

	1	2
Test significance level, α	0.05	0.05
1 or 2 sided test?	1	1
First condition mean, μ_1	2.0	
Second condition mean, μ_2	2.5	
Mean difference, $\mu_d = \mu_1 - \mu_2$	-0.5	
Standard deviation of differences, σ_d	1.0	
Effect size, $\delta = \mu_d / \sigma_d$	0.5	0.5
Power (%)	80	80
N	27	27

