15.2. STATISTICAL METHODS

Study Population:

Intent-to-treat (ITT) population – all patients enrolled to the study who received at least one treatment.

Per Protocol (PP) population - all patients in the ITT population who completed the study according to the protocol and with no major protocol violations.

General

All measured variables and derived parameters will be listed individually and, if appropriate, tabulated by descriptive statistics. For categorical variables, summary tables will be provided giving sample size, absolute and relative frequency and 95% CI (Confidence Interval) for proportions by study arm. For continuous variables, summary tables will be provided giving sample size, arithmetic mean, standard deviation, median, minimum and maximum and 95% CI (Confidence Interval) by study arm for means of variables.

All tests will be two-tailed, and a p-value of 5% or less will be considered statistically significant.

The data will be analyzed using the SAS ® version 9.3 (SAS Institute, Cary North Carolina).

Periodontal pockets treated with Pocket-X Gel will be analyzed vs.control pockets.

Efficacy assessment

The following efficacy parameters will be summarized in appropriate tables by treatment and visit. Changes from baseline will be summarized as well.

- Pocket probing depth
- Bleeding index
- Recession level
- Clinical attachment level
- Mobility grade
- Furcation
- Specific periodontal bacteria quantification [optional]

The Paired T-test or Signed rank test for two means (paired observations) (as is appropriate) will be applied for analyzing the calculated changes by time point within each treatment.

The Paired T-test or Signed rank test for two means (paired observations) (as is appropriate) will be applied for analyzing the difference in the above measurements and changes between the treatments.

Responder will be defined based on improvement of gingival healing and natural sealing of periodontal pockets. Chi-square test or Fisher's Exact test (as is appropriate) will be applied for comparing the proportion of responders between the tested and the control segments.

The efficacy results will be compared also to literature data, if available. The two-sample T-test or Non-parametric Wilcoxon-Mann-Whitney Rank sum test for independent samples (as is appropriate) will be applied for comparative analysis.

Safety assessment

Safety assessments will be based on Adverse Events (AEs) and oral inspections recorded at each visit.

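### Section 15.2 does not fix the unit of analysis: the named paired tests are worded for pockets, while 15.1 assumes one difference per patient, and run on pockets they do not reliably hold 5%

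*Combined protocol and SAP*

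**What the plan says.** Section 9.1 sets the level of recording: "The values will be recorded separately for each periodontal pocket". It then words the comparison at the same level: "The efficacy results will be compared between treated periodontal pockets and control periodontal pockets". Section 15.2 repeats this under its general rules: "Periodontal pockets treated with Pocket-X Gel will be analyzed vs.control pockets".

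For the efficacy measurements, 15.2 names a paired t-test or signed-rank test twice. The first use is for changes over time within each treatment. The second, in the plan's words, "will be applied for analyzing the difference in the above measurements and changes between the treatments". It also promises 95% confidence intervals for means by study arm. It does not say what one observation, or one pair, is in any of these.

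Section 15.1 works at a different level. Its aim is "demonstrating a difference in change in pocket depth between the tested segments and the control", and it counts people: "34 subjects will be recruited, in order to have 27 participants who complete the study". The analysis populations are also defined by patients; the ITT set is "all patients enrolled to the study who received at least one treatment".

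Inclusion criterion 4 in 6.1 requires at least 3 sites of 5 mm or deeper in every quadrant, so each patient contributes several pockets to each condition. Section 3.3 gives the within-mouth comparison, "while the contralateral segment(s) of the mouth will serve as control", and 5.1 says the same. No available passage matches individual pockets across the two sides, gives an averaging rule, or names a method for clustered data.

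**The concern.** A paired t-test or signed-rank test treats its differences as independent. One difference per patient meets that condition. Several pocket differences from the same mouth may not, because pockets share a patient, a side and a quadrant. If they are entered as separate observations, the standard error is computed from the wrong number of independent units.

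The p-values and intervals for the trial's efficacy claims are at stake. The by-arm intervals and within-treatment tests are exposed to any difference between patients. The between-treatment test is exposed only to variation that pairing does not cancel, and there the error can go either way. In an open-label study, an unstated unit also leaves room to choose it after the data have been seen.

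**Working it through.** **1. The plan's own figure.** Inputs from 15.1: effect size 0.5, one-sided 5%, paired t-test. With n independent differences, power comes from the noncentral t distribution with n − 1 degrees of freedom and noncentrality 0.5 × √n.

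- n = 26: 79.8%
- n = 27: 81.2%
- Dropout: 27 / (1 − 0.20) = 33.75, rounded up to 34

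So 27 and 34 reproduce, with exactly one difference per participant. (15.1 is one-sided and 15.2 two-tailed; that is a separate matter.)

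**2. Assumptions for a pocket-level run.** The documents give no variance components and no pocket matching, so everything in this step is assumed. Total variance of a pocket's change is 1, with 0.15 between patients, s between sides within a patient (0, 0.05, 0.10 or 0.20), and the remaining 0.85 − s between pockets. There are m pockets per condition, equal in number and paired one to one. The value m = 3 is the eligibility minimum for one treated quadrant, and m = 6 for two. Two-sided type I error at nominal 5% is approximately 2 × [1 − Φ(1.96/√D)], where D is the true variance of the mean divided by the variance the test assumes.

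**3. Within-treatment tests and by-arm intervals, s = 0.** The patient effect does not cancel. The correlation between a patient's pockets is 0.15, and D = 1 + (m − 1) × 0.15.

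- m = 3: D = 1.30, type I error 8.6%, standard error too small by 1 − 1/√1.30 = 12%
- m = 6: D = 1.75, type I error 13.8%, standard error too small by 1 − 1/√1.75 = 24%

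Nominal 95% intervals would then cover about 100 − 8.6 = 91.4% and 100 − 13.8 = 86.2%. Simulations gave 8.2-8.6% and about 14%.

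**4. Between-treatment test.** The patient effect cancels in each pocket difference. What remains correlated is the side effect, with ρ = s / (s + pocket variance) = s / 0.85.

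- Pockets all on one side: D = 1 + (m − 1)ρ.
- Two treated quadrants on a diagonal with a left/right effect: the effect enters the two quadrant differences with opposite signs. Each of 6 pocket differences is correlated +ρ with 2 others and −ρ with 3, so D = 1 + 2ρ − 3ρ = 1 − ρ.

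| s | ρ | 3 per side: D, error | 6, same side: D, error | 6, diagonal: D, error |
|---|---|---|---|---|
| 0 | 0 | 1, 5.0% | 1, 5.0% | 1, 5.0% |
| 0.05 | 0.059 | 1.118, 6.4% | 1.294, 8.5% | 0.941, 4.3% |
| 0.10 | 0.118 | 1.235, 7.8% | 1.588, 12.0% | 0.882, 3.7% |
| 0.20 | 0.235 | 1.471, 10.6% | 2.176, 18.4% | 0.765, 2.5% |

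Null simulations of 27 patients (200,000 runs per setting) gave 6.4%, 7.7% and 10.6% for 3 per side, and 8.4%, 12.0% and 18.6% for 6 on one side. Smaller simulations of the diagonal layout gave 4.1-4.3%, 3.7-3.8% and 2.5-2.7%. A pocket-level signed-rank test behaved like the t-test in the same-side layouts (6.1-10.2% and 8.4-17.8%). If the shared variation belongs to each quadrant rather than the whole side, two quadrants of 3 pockets give D = 1 + 2ρ, the 3-pocket column.

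**5. Patient-level run.** With one mean difference per patient, the paired t-test stayed at 4.9-5.0% in the 200,000-run between-treatment simulations.

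**The case against.** The best case for the plan is that it already means a patient-level analysis. Both tests are described as being for paired observations, and the only pairing the documents supply is treated against contralateral segments within a patient. Section 15.1 defines the effect on that contrast, the populations consist of patients, and 15.2 allows derived parameters. A pocket-level paired test could not be run without inventing a matching rule. On this view, the sentence about pockets only says which sites are compared.

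Much of this stands: the patient-level reading is plausible, and the paired test is valid under it. It does not close the gap. The sentences that word the comparison, in 9.1 and 15.2, both name pockets. Even at patient level, the plan does not say which pockets enter a patient's value or how they are combined. Nor is the control set fully fixed: 5.2 leaves two or three quadrants untreated, and section 4 compares with untreated segments without limiting them to the contralateral ones.

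A reader might infer that the planned test is certain to be anti-conservative. The documents do not support that. The between-treatment test holds 5% if there is no side-specific correlation. It falls below 5% in the diagonal layout with a left/right effect, and no passage requires two treated quadrants to be on the same side. A reader might also quote the 18% figure as the trial's error rate, but it needs 6 matched pockets on one side and an assumed 20% side variance.

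Finally, every segment receives scaling and root planing, so rejecting no change within a treatment is of limited interest. In that part of the plan, the narrow intervals matter more than the test.

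**Conclusion.** The point holds as an unstated unit of analysis with real consequences if 15.2 is followed as worded. It is not a demonstrated error in a patient-level paired test, and the documents do not show that a pocket-level test will be run.

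Run on pockets, the within-treatment tests and by-arm intervals are too liberal whenever patients differ. The between-treatment test is too liberal in the same-side layouts with side-specific correlation, and conservative in the diagonal layout. The sizes in the working rest entirely on assumed variances, equal pocket counts and one-to-one matching, so the documents settle neither the size nor, for the between-treatment test, the direction. This should be fixed before analysis. It gives no reason to change 27 or 34, which already presume the patient as the unit.

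**What to change.** State in 15.2 that the patient is the unit of analysis for the within-treatment tests, the between-treatment tests and the confidence intervals. For each patient, average the change from baseline over a pre-specified set of baseline pockets, once over the gel segment(s) and once over the contralateral control segment(s) only. Apply the paired t-test or signed-rank test to the one value per patient within a treatment, and to the one difference per patient between treatments, as 15.1 assumes. A mixed model with random effects for patient and for segment or side within patient is an acceptable alternative. Bring the wording of 9.1 into line.

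The cost is a few sentences and a little programming. No new data are needed, and the sample size is unaffected by this change. The drawback for the sponsor is that results may look less significant than they would in a pocket-level test.

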5. STUDY DESIGN

5.1. OVERALL DESIGN

This study is a single arm, open-label, split-mouth study.

All enrolled participants will initially undergo root planing and scaling on the entire mouth. Following the completion of scaling and root planing, each participant will have one/two of his/her mouth segments (quadrants) treated with Pocket-X Gel. The contralateral segment(s) of the Pocket-X Gel-treated segment(s) will serve as control.

The study hypothesis is that patients treated with Pocket-X Gel following scaling and root planing will exhibit better periodontal pocket healing on their treated segment(s) than their untreated segment(s) as well as compared to data available in the literature concerning the efficacy of scaling and root planing.

The total duration of the study for each participant will be 6-7 months. The study will include a total of 5-7 visits, depending on the number of scaling and root planing sessions required,

based on the severity of each participant's periodontal disease. Follow-up visits will occur 4, 12 and 24 weeks after completion of scaling and root planing and first application of the studied device. Detailed description of each visit is provided under section 5.5 – Visits and Follow-Ups.

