9.2. SAFETY ASSESSMENT

Safety assessment will be conducted based on adverse events reported by the study participants as well as any new pathologies observed by the investigators during visits that did not exist at baseline or have worsened since baseline. Such observations will also be regarded as adverse events.

Safety assessment will be conducted by analyzing the adverse events, their quantity, severity, duration and their connection to the studied device. In case that the adverse event is localized, these parameters will be compared between the segment(s) treated with Pocket-X Gel and the untreated segments of the same patient. Adverse events will also be compared to adverse events reported during scaling and root planing studies, based on available literature.

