All AEs will be coded using coding dictionaries MedDRA (most updated version) and will be

summarized by system organ class (SOC) and preferred term (PT).

AEs will be listed individually including SOC, PT, seriousness of event, onset and resolution dates, duration, severity, relationship to the study treatment, action taken and outcome.

Frequency AEs and treatment-related adverse events will be summarized in tables by SOC, PT and treatment and by seriousness.

In case that the adverse event is localized, frequency of local AEs will be compared between the segment(s) treated with Pocket-X Geland the untreated segments of the same patient using Chi-square test or Fisher's Exact test (as is appropriate).

Adverse events will also be compared to adverse events reported during scaling and root planing studies, based on available literature. Chi-square test or Fisher's Exact test (as is appropriate) will be used for comparison in incidence of events.

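### Responders and local adverse events are compared within the same mouth by Chi-square or Fisher tests, which assume independent groups; no paired binary test is named

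*Combined protocol and SAP*

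**What the plan says.** Section 5.1 describes a single-arm split-mouth study: "The contralateral segment(s) of the Pocket-X Gel-treated segment(s) will serve as control". Every participant therefore contributes to both sides of each comparison.

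Section 15.2 uses this for the listed measurements. The between-treatment comparison is by paired t-test or signed rank test: "Signed rank test for two means (paired observations) (as is appropriate) will be applied for analyzing the difference in the above measurements" and their changes.

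The binary endpoints are handled differently:

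- **Responders (15.2, Efficacy assessment):** the comparison is of segments: "Chi-square test or Fisher's Exact test (as is appropriate) will be applied for comparing the proportion of responders between the tested and the control". Responder status itself is described only in these terms: "Responder will be defined based on improvement of gingival healing and natural sealing of periodontal pockets", with no measure, cut-off, visit or unit.
- **Local adverse events (15.2, Safety assessment):** frequency is compared between gel-treated and "untreated segments of the same patient using Chi-square test or Fisher's Exact test (as is appropriate"). Section 9.2 agrees: "these parameters will be compared between the segment(s) treated with Pocket-X Gel and the untreated segments of the same patient".

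The unit of analysis varies. The responder sentence speaks of segments. The General part of 15.2 says "Periodontal pockets treated with Pocket-X Gel will be analyzed vs.control pockets", and section 9.1 says "The efficacy results will be compared between treated periodontal pockets and control periodontal pockets". Under section 5.2, one or two quadrants are treated and two or three are left untreated.

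**The concern.** Pearson's Chi-square and Fisher's exact test treat the two groups as independent. Here the test and control sides share the same patient, hygiene, disease severity and operator. The qualifier about appropriateness only chooses between these two tests, and neither is paired. The paired tests earlier in 15.2 apply to the measurements listed above them. Responder status is introduced afterwards with its own test.

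The consequence depends on the unit, which the plan leaves open:

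- With one result per side and positive within-mouth correlation, the planned tests overstate the variance of the difference. They become conservative and give up the power that a split-mouth design is meant to provide.
- With pockets entered as independent rows, clustering of pockets within a side can outweigh that effect and produce too many false positives.

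The adverse event comparison has a further problem. Its comparator is all untreated segments, not only the contralateral control, so the two sides can differ in the number of quadrants at risk.

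**Working it through.** **1. The plan's own figure.** Section 15.1 gives 27 completers for a paired t-test with effect size 0.5, 80% power and one-sided 0.05. The noncentral t distribution gives 79.8% power at N = 26 and 81.2% at N = 27, so 27 reproduces. With 20% dropout, 27/0.8 = 33.75, rounded up to 34. This calculation concerns change in pocket depth, so the point below does not alter it.

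**2. Why pairing matters.** For one yes/no result per side in n participants, with within-participant correlation phi,

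Var(p1 − p0) = [p1(1−p1) + p0(1−p0) − 2·phi·√(p1(1−p1)·p0(1−p0))]/n.

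Chi-square omits the phi term. Under equal proportions the true variance is (1 − phi) times the one it assumes, so its effective critical value is 1.96/√(1 − phi). At phi = 0.33 this is 1.96/√0.67 = 2.39, a two-sided error of about 1.7% in place of 5%. Exact enumeration, which allows for discreteness, gives 1.3% (next table).

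**3. Exact enumeration.** All 27-pair tables were enumerated at two-sided 5%, the level set in section 15.2. Responder rates and correlations are assumptions. Correlation comes from a latent Gaussian model with rho 0/0.3/0.5/0.7.

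Null error (%), 50% responders on both sides:

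| phi | 0 | 0.19 | 0.33 | 0.49 |
|---|---|---|---|---|
| Chi-square | 4.2 | 2.4 | 1.3 | 0.5 |
| Fisher | 2.2 | 1.1 | 0.5 | 0.2 |
| McNemar, asymptotic | 4.5 | 4.3 | 4.3 | 4.6 |
| McNemar, mid-p | 4.5 | 4.2 | 4.0 | 3.5 |

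At 30% or 70% responders, with phi 0/0.18/0.32/0.48, Chi-square gives 5.4/3.4/2.1/0.9% and asymptotic McNemar 4.3/4.3/4.4/4.8%.

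Power (%), 70% against 45%:

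| phi | 0 | 0.18 | 0.31 | 0.44 |
|---|---|---|---|---|
| Chi-square | 44.3 | 43.8 | 43.2 | 42.2 |
| Fisher | 34.3 | 32.8 | 31.4 | 29.4 |
| McNemar, asymptotic | 43.6 | 50.1 | 57.2 | 68.5 |
| McNemar, mid-p | 43.5 | 50.0 | 56.9 | 66.9 |
| McNemar, exact | 34.6 | 40.3 | 46.4 | 55.1 |

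Asymptotic McNemar minus Chi-square is −0.7, +6.3, +14.0 and +26.3 points. Exact McNemar is below Chi-square at phi 0 and 0.18.

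**4. One illustrative data set.** Take 27 pairs: 10 respond on both sides, 8 on the test side only, 1 on the control side only, 8 on neither.

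- The margins are 18/27 and 11/27. Chi-square = 54·(18·16 − 9·11)²/(27·27·29·25) = 3.65, p = 0.056. Fisher gives p = 0.101.
- Exact McNemar uses the 9 discordant pairs: 2·(1 + 9)/2⁹ = 0.039. Asymptotic McNemar: (8 − 1)²/9 = 5.44, p = 0.020.

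The same data fall on opposite sides of 5%.

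**5. If pockets are pooled as rows.** This is a simulation with 27 participants, 50% responders, a probit model, patient SD 0 to 1 and 20,000 trials per setting. Section 6.1 gives only a minimum of 3 qualifying sites per quadrant; all other inputs are assumed. Chi-square null error (%), range over patient SD:

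| Pockets per side | side SD 0 | side SD 0.25 | side SD 0.5 |
|---|---|---|---|
| 3–6 | 1.7–5.2 | 2.2–7.2 | 3.6–12.9 |
| 10 | 1.8–5.2 | 3.9–9.4 | 10.9–18.6 |

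The error can go either way.

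**6. Local adverse events.** At an assumed 15% against 5%, one result per side and phi 0 to 0.36, every test is weak: Chi-square 18–24%, Fisher 4–7%, asymptotic McNemar 21–27%, mid-p 14–15%, exact 6–8%. No power gain over Chi-square is claimed. Balance is a separate matter. At an assumed independent 5% risk per quadrant, one gel quadrant has an event with probability 5%. At least one of three untreated quadrants does so with probability 1 − 0.95³ = 14.3%, with no device effect at all.

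**The case against.** The best defence is that little rests on this. The trial is sized on pocket depth, and the listed measurements already have paired tests. On the unit named in the responder sentence, with one result per side, the error is conservative: a real effect may be missed, but a false claim is not made more likely. That stands and limits the severity.

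The size of the gain is also unknown. It runs from about −1 to +26 points, and the upper end needs a strong within-mouth correlation that the documents do not support or exclude. That stands too. Confidence belongs to the mismatch of test and design, not to any single power figure.

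The inflated error requires pockets to be pooled, against the responder sentence's reference to segments. It is a conditional risk, kept open by the pocket wording in 9.1 and in the General part of 15.2. That wording is not specific to the binary endpoints.

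The adverse event part is weaker. One result per side costs no clear power there, the plan does not specify an any-event count, and two treated against two untreated quadrants would be balanced in number. The comparison with literature adverse event rates involves separate groups and is not affected.

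None of this makes an independent-groups test suitable for comparing two sides of one mouth.

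**Conclusion.** The concern holds. Section 15.2 prescribes independent-groups tests for two within-mouth binary comparisons in a split-mouth trial and names no paired or clustered alternative. This is a rule that conflicts with the design, not merely missing detail.

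For responders with one result per side, the loss is nil near zero correlation. At moderate correlation (phi about 0.3) it is roughly 14 points of power for 70% against 45%, all on assumed rates. If pockets are pooled, the error may be too low or too high, depending on how strongly pockets on one side cluster. For local adverse events the case rests on matching the analysis to the design and on balanced exposure, not on power.

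This should be fixed before analysis. It does not threaten the sample size or the paired tests of the listed measurements.

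**What to change.** In section 15.2:

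- **Responders.** Fix the measure, cut-off, visit and unit, including how two segments on one side combine. Form one result per side per participant. Replace Chi-square/Fisher with one pre-specified McNemar test (asymptotic or mid-p), reported with the paired difference in proportions and its 95% CI.
- **If several pockets or segments per side are kept.** Analyse each participant's difference in side proportions by paired t-test or signed rank test (simulated null error 4.7–5.1% and 4.2–5.3%). Participant-clustered GEE with a Mancl-DeRouen correction is an alternative (4.9–5.7%; uncorrected 5.9–6.6%). Choose one in advance.
- **Local adverse events.** Compare with the contralateral control segment(s) only, or use a per-segment denominator, and apply the same paired approach.
- **Literature comparison of adverse events.** The pairing point requires no change.

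The cost is SAP wording, a responder definition agreed before analysis, and standard SAS code such as PROC FREQ with the AGREE option. No new data are needed and N does not change. If within-mouth correlation proves to be near zero, there is little or no gain in power.

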4. OBJECTIVES

The overall objective of this study is to assess the safety and efficacy of Pocket-X Gel in the improvement of gingival healing and natural sealing of periodontal pockets in patients with periodontal disease, following scaling and root planing. Safety will be evaluated in accordance with the adverse events reported by participants and oral pathologies recorded by the investigators, compared between segments treated with the studied device and segments untreated with the studied device (in case of localized adverse events) and to adverse events attributed to scaling and root planing based on available literature. Efficacy will be determined in respect to the differences between the measurements taken from segments treated with the studied device and segments that were not treated with the studied device, also taking into account efficacy measurements from similar studies and studies on scaling and root planing, based on available literature.

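### The planned significance tests of efficacy against published results cannot deliver a valid p-value: the rank-sum test needs data the plan does not provide for, and the two-sample t-test ignores differences between studies

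*Combined protocol and SAP*

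**What the plan says.** Section 15.2, under efficacy assessment, first sets out paired tests of treated against control segments. It then adds: "The efficacy results will be compared also to literature data, if available". The method follows: "The two-sample T-test or Non-parametric Wilcoxon-Mann-Whitney Rank sum test for independent samples (as is appropriate) will be applied for comparative analysis". The general rule in the same section covers these tests too: "All tests will be two-tailed, and a p-value of 5% or less will be considered statistically significant".

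Three other sections refer to the same comparison:

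- Section 5.1 puts it in the study hypothesis. Healing is to be better than in the untreated segments, "as well as compared to data available in the literature concerning the efficacy of scaling and root planing".
- Section 4 puts it in how efficacy is determined, "also taking into account efficacy measurements from similar studies and studies on scaling and root planing, based on available literature".
- Section 9.1 repeats it: "The efficacy results will be compared between treated periodontal pockets and control periodontal pockets and to data obtained from available literature".

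The design already contains a concurrent comparator. Section 5.1 says "This study is a single arm, open-label, split-mouth study" and "The contralateral segment(s) of the Pocket-X Gel-treated segment(s) will serve as control".

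The documents do not say which published studies will be used, how or when they will be chosen, or whether individual patient data will be sought. They do not give the unit of analysis, or say whether gel or control segments are set against the literature. They make no allowance for variation between studies.

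**The concern.** The two tests fail for different reasons.

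The rank-sum test orders every individual value in both groups. A published mean, SD and sample size do not supply those values, and the plan has no provision for obtaining them.

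The two-sample t-test can be computed from published summaries. Its standard error, however, reflects only the sampling of patients within each study. Any difference in population, baseline depth, operators, examiners or follow-up goes into the numerator and is read as treatment effect. The examiner calibration in section 10 covers this trial's two examiners and cannot extend to a published study. With no rule for choosing papers, parameters or visits, the room for a chance finding is wider still.

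At stake is a p-value that section 15.2 would call significant, on a comparison that section 5.1 names in the hypothesis. It could be reported as evidence that the gel is superior to scaling and root planing (SRP), although the test cannot separate a gel effect from a difference between studies.

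**Working it through.** **1. The plan's own figure.** Section 15.1 gives 27 completers for a paired t-test with effect size 0.5, one-sided 5% level and 80% power, and 34 recruited. The noncentral t distribution gives power 79.8% at N = 26 and 81.2% at N = 27, so 27 reproduces. Dropout: 27 / (1 − 0.20) = 33.75, rounded up to 34. The documents give no sample size or power for the literature comparison.

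**2. Rank-sum test on summaries.** Take 27 trial values with mean 2.4 and SD 1.0. Compare them with three constructed literature samples, each with n = 100, mean 2.0 and SD 1.0, that differ only in shape.

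| Shape of literature sample | t-test p | Rank-sum p |
|---|---|---|
| Normal | 0.068 | 0.077 |
| Right-skewed | 0.068 | 0.0075 |
| Left-skewed | 0.068 | 0.16 |

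The published summary is the same in all three rows, but the rank-sum result falls on either side of 5%. It cannot be recovered from mean, SD and n.

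**3. Error rate of the two-sample t-test.** Every input except the 27 completers is an assumption:

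- No gel effect.
- Patient-level SD of change 1.0 mm. The 1.0 in section 15.1 is the SD of within-patient differences, which is a different quantity.
- Literature sample of 50 or 200.
- SD of the gap between the two study means, τ, of 0.2, 0.3 or 0.5 mm.

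The test uses SE² = 1/27 + 1/n. The true variance of the difference is SE² + τ². By the normal approximation,

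error = 2 × [1 − Φ(1.96 × SE / √(SE² + τ²))].

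For n = 50: SE² = 0.0370 + 0.0200 = 0.0570, so SE = 0.239. With τ = 0.3, the square root is √(0.0570 + 0.0900) = 0.383, the ratio is 0.623, and 1.96 × 0.623 = 1.22. The error is 22.2%.

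For n = 200: SE² = 0.0370 + 0.0050 = 0.0420, so SE = 0.205.

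By symmetry, half of each two-sided rate is false superiority (nominal 2.5%).

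| n | τ (mm) | Two-sided error | False superiority |
|---|---|---|---|
| 50 | 0.2 | 13.3% | 7% |
| 50 | 0.3 | 22.2% | 11% |
| 50 | 0.5 | 39.8% | 20% |
| 200 | 0.2 | 16.1% | 8% |
| 200 | 0.3 | 26.9% | 13% |
| 200 | 0.5 | 45.7% | 23% |

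**4. If each study mean varies.** The table treats τ as the SD of the gap. If the trial mean and the published mean each vary with SD τ, the gap has variance 2τ². The two-sided rates are then about 21%, 34% and 53% (n = 50) and 25%, 39% and 59% (n = 200). A simulation of this version at n = 100 and τ = 0.3 gave 36.9% in total and 18.4% in favour of the gel. The formula with a t reference gives 36.9% and 18.5%.

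**5. Sensitivity to the patient SD.** With n = 100 and a gap SD of 0.3 mm, the two-sided rate is 24.8% at patient SD 1.0 mm and 36.9% at 0.71 mm. At τ = 0 it is 5% in every case.

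**The case against.** The strongest reply is that this is a side comparison. Section 15.2 introduces it with *also* and makes it depend on availability. The sample size rests only on test against control segments. Section 3.3 states the hypothesis against pockets treated by SRP alone, with no mention of literature. All of that stands, and it limits the weight of the point.

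A reader might infer that a significant literature p-value could confirm the study hypothesis even if the within-mouth contrast failed. The documents do not support that. The hypothesis in section 5.1 joins the two comparisons, so failure against the untreated segments means it is not met. A reader might also infer that the papers will be picked after the results are known. The plan is silent on when and how they are chosen, and silence does not show that.

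The two-sided rates should not be read as rates of false superiority, because half of each is false inferiority and the bias can run either way. No document supplies a value for τ, so the figures show the direction and possible scale of the problem and are not an estimate for this trial.

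What the reply does not remove is that section 15.2 specifies a formal test under the 5% rule, and nothing elsewhere says its result is for context only.

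**Conclusion.** The point holds as a secondary defect. One of the two named tests cannot be carried out on published summaries. The other can be carried out, but its p-value lacks its nominal error rate as evidence of a gel effect. On the assumptions shown, false superiority over a published result would occur in about 7% to 23% of cases instead of 2.5%, and more often if both study means vary. The result depends on τ, and the inflation disappears only if τ is zero.

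The paired split-mouth analysis and the 27 completers are not affected. The matter still deserves correction because the hypothesis, the objective and the efficacy assessment all refer to the literature comparison, and its p-value could be reported as evidence of superiority over SRP.

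**What to change.** - In section 15.2, delete the two-sample t and rank-sum tests against literature. Present published SRP results in a descriptive table beside the trial's estimates and 95% confidence intervals, without p-values.
- Set in advance the rule by which published studies are selected.
- In sections 4, 5.1 and 9.1, state that the efficacy conclusion rests on the within-mouth paired contrast and that literature serves as context only.
- Treat the chi-square or Fisher comparison of adverse events with literature, in the safety part of section 15.2, the same way. It has the same weakness.

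The cost is wording only. No patients, visits or measurements are added, and the 27 completers and 34 recruited do not change on this account. The sponsor gives up a p-value that has no controlled error rate.
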